#### SUMMARY OF ACTIONS TO BE TAKEN ON THE DISEASE RESPONSE WITH EACH CYCLE

Response	Action	Notes
Complete Response (CR)	-	-
Partial Response (PR) / Stable Disease (SD)	If available, administer another cycle of adimleculeucel from the same cell line and reassess	Maximal response is a PR after 3 consecutive PR responses; after maximal response (3 cycles resulting in PRs), then observe
Stable Disease (SD)	If SD is the first Cycle response, administer the same adimleculeucel cell line for the next cycle and reassess; if SD is the second Cycle response, administer a different adimleculeucel cell line from a different donor (Switch Therapy) for the next cycle and reassess	If the subject has SD after 2 cycles of the same adimleculeucel cell line, a different adimleculeucel cell line may be administered (Switch Therapy)

Progressive Disease (PD)	Subsequent Cycles of adimleculecel with different restricting HLA alleles from a different donor(Switch Therapy)	If Switch Therapy results in CR/PR/ SD continue with subsequent cycle of adimleculecel from the same donor, then observe. If Switch Therapy results in PD, discontinue therapy.
--------------------------	--	--

All subjects receiving antiviral drugs can remain at their current dose during the adimleculecel treatment period. Subjects may also continue treatment with rapamycin and calcineurin inhibitors. Corticosteroid doses should be reduced to the lowest acceptable dose; adimleculecel has not been administered with prednisone-equivalent daily doses > 0.5 mg/kg.

## **9.2 Subjects**

Subjects will include patients treated with adimleculecel derived from third party donors. This will include recipients of allogeneic hematopoietic cell transplant recipients, solid organ transplant (SOT) recipients, human immunodeficiency virus, other immunocompromised states, and immune competent subjects with persistent CMV infection or viremia.

## **9.3 Selection of Adimleculecel**

Patients will receive adimleculecel selected from our bank of GMP grade adimleculecel lines generated from normal HCT donors specifically consented for this purpose. The third party adimleculecel to be administered will be evaluated on the basis of 2 criteria: 1) they share at least one HLA allele with the patient, and 2) they are restricted by at least one HLA allele shared by the patient.

## **10.0 EVALUATION DURING TREATMENT/INTERVENTION**

The schedule of tests described should be adhered to whenever possible. However, in certain situations, particularly late after treatment, circumstances may preclude assessments at the times specified, at which point they may be held at the discretion of the treating physician:

### **10.1 Treatment Cycle**

#### **10.1.1 Treatment days**

Patients will have vital signs assessed prior to each infusion, immediately after the infusion, and at hours 1, 2 and 4 after each infusion (+/-) 10 minutes.

On Days 0, 7 [ $\pm$  2 days], and 14 [ $\pm$  2 days] of each cycle, perform the following assessments: prior to the infusion.

- History, Review of Systems and Physical Exam (including GvHD assessment for cycle 1 only. For patients receiving more than 2 cycles, GvHD assessment will occur at the start of each cycle only.).

- Assessment of SAEs and anti-viral and immune suppressive concomitant medications
- Assessment of CRS and ICANs per institutional standards
- CMV DNA quantitation by PCR

## 10.2 Follow-up

### 10.2.1 Monitoring during the first 8 weeks

Patient will be monitored for eight weeks after administration of the first dose of adimleculeucel. During this period, perform the following:

- Assessment of SAEs and concomitant medications
- Assessment of CRS and ICANs per institutional standards
- CMV DNA quantitation by PCR to determine if an additional cycle is needed
- Assessment/Phone assessment for symptoms of GvHD weekly at baseline and prior to each infusion, week 5 (Day 28 – 32) if patient not receiving subsequent cycles of CMV-CTLs
- The timing of Consensus GvHD assessments is dependent on the number of infusions patients receive and will be performed as per institutional standards.

For patients who receive subsequent cycles of cells, the monitoring calendar will re-start with the first dose of the subsequent cycle, with the exception of GvHD assessments, which will occur as above.

### 10.2.2 Safety follow-up 30-35 days after the last dose

The safety follow-up visit should occur at the center 30-35 days after the last dose of adimleculeucel. At this visit, the following is required:

- Assessment of SAEs and concomitant medications
- Assessment of CRS and ICANs per institutional standards
- CMV DNA quantitation by PCR to determine if an additional cycle is needed

### 10.2.3 Follow-up at 90 and 180 days after the last dose

Follow-up visits will be performed at 90 ( $\pm$  14) days and 180 ( $\pm$  30) days after administration of the last dose of adimleculeucel. At these visits, perform the following:

- CMV DNA quantitation by PCR
- Survival status
- Consensus GvHD assessments as per institutional standards.

If the CMV infection affects the CNS, lung, or abdominal organs, and virus has been detected (e.g.: in pleural or peritoneal fluids), appropriate tissue and/or CSF may be collected (if indicated and possible) and tested for the presence of CMV and CMV specific T-cells. These tests should occur between 3-6 weeks post initiation of treatment, whenever possible.

APPROXIMATE SCHEDULE OF PATIENT EXAMINATIONS AND STUDIES

Evaluation	Prior to CMV CTLs	Infusion 1	Infusion 2	Infusion 3	Wk 3	Wk 4	Wk 5	Week 6-7 ab / Safety Follow-up 30-35 days after last dose	Wk 8	Mo 3 Follow-up 90 ± 14 days after last dose	Mo 6 Follow-up 180 ± 30 days after last dose
		Day 0	Day 7 (± 2 days)	Day 14 (± 2 days)	Day 21	Day 28	Day 35	Day 44-49	Day 56		
ICF signed	X										
Inclusion/exclusion criteria	X										
Medical history	X										
Weight	X										
Hematology and serum chemistry c	X										
Pregnancy test d	X										
High resolution HLA typing for subject e	X										
Chest X-Ray f	X										

Vital signs	X	X g	X g	X g							
ATA230 Treatment h		X	X	X							
Physical Exam	X	X	X	X				X		X	X
Concomitant medications	X	X	X	X	X b	X b	X b	X	X b	X b	
CMV DNA by PCR i	X	X	X	X	X	X	X	X	X	X	X
SAEs j	X	X	X	X	X	X	X	X	X		
GvHD k	X	X	X	X			X b				
Consensus GvHD CRS and ICANS l							X				AS PER INSTITUTIONAL STANDARDS
Survival status										X	X

Evaluations below are to be performed as clinically indicated:

Physical Exam					X	X	X		X		
Hematology and serum chemistry c	X	X	X	X	X	X	X	X	X	X	X
CT Scan	X										
Ophthalmology scan, Colonoscopy, Cultures of affected body fluids or tissues	X	X	X	X	X	X	X	X	X	X	X
ECHO/EKG	X										
T cell immunophenotype short panel	X			X				X		X	X
Mitogens (PHA)				X				X		X	X
Antigen Specific Proliferation	X			X				X		X	X

a The Safety in-person follow-up visit will overlap with the weekly follow-up visit during week 6 or 7. Evaluate CMV DNA weekly during both weeks. Perform assessment of CRS and ICANs per institutional standards to align with FACT requirements

b Evaluation may be completed by phone

c CBC & CMP

d For women of childbearing potential

e In addition, as available through medical records, high resolution HLA typing of the allograft donor for alloHCT recipients or low resolution HLA typing of the organ donor for SOT recipients

f Per section 8, not necessary if CT scan is done

g On each dosing day, monitor vital signs prior to the infusion, immediately after the infusion, and at 1, 2 and 4 hours ( $\pm$  10 minutes at each time point) following initiation of the infusion

h If patient is given additional cycles of ATA230, calendar will restart from Day 0. Doses are given weekly and can be held at the discretion of the PI or in the case of severe toxicity related to infusion

i Tests quantitating CMV viremia by CMV DNA copies per milliliter of blood should be obtained weekly for the first 8 weeks post-initial infusion with CMV-specific T-cells, and then at approximately monthly intervals until 6 months post infusion

j Any adverse events observed at screening, should be included as medical history

k GvHD evaluations to be performed at pretreatment, baseline (D1) and weekly (D7 and D14) for the first 3 infusions. Then week 5 (Day 28 – 32). For patients receiving more than 2 cycles: baseline at the start of each cycle.

l GvHD consensus to be performed on Day 30 from the first infusion and at 100 ( $\pm$  10) days post first CMV CTL infusion of last cycle

## 11.0 TOXICITIES/SIDE EFFECTS

One of the primary objectives is to continue to identify the risk of development or flare of pre-existing graft versus host disease.

**Graft versus Host Disease.** The CMV peptide-specific T-cells have been cultured for over 4 weeks. During this time, T-cells reactive against other antigens, including alloantigens that might be expressed by tissues in the patient, die off and are deleted. The T-cells to be infused will be tested and shown to have no significant activity against normal allogeneic cells prior to their infusion. However, there is a finite risk that small numbers of alloreactive T-cells could be transferred in the T-cell inoculum, which could cause Graft versus Host Disease (GvHD). In patients treated with third party-derived virus-specific T-cells, this risk could be increased. This immune reaction against the host can cause skin rash, hepatitis, and enteritis. In its most severe form, it can be fatal. Were moderate to severe GvHD (Grade 2-4) to develop, the patient will be treated with high doses of glucocorticosteroids. Additional immunosuppressive agents may be used if the GvHD does not respond to steroid treatment. Patients who might subsequently receive donor lymphocytes, boosts, or a secondary transplant will be evaluable up until that time point.

In Protocols 95-024, 05-065, 11-130, and 12-086, and 14-070 of subjects are evaluated for the occurrence of GvHD for 100 days. A total of 4 patients have developed de novo GvHD one after EBV-CTLs and 3 after CMV-CTLs. GvHD in these patients was as skin GvHD in 3 patients and gastrointestinal GvHD in 1 patient. Two cases were considered unlikely related to third party viral specific CTLs and two possibly related. An additional 11 subjects, with a history of GvHD, had GvHD after administration CTL administration; these cases were considered unrelated or unlikely related to CMV-CTLs.

In this study, we will be capturing and tracking Grade 3-5 toxicities which occur within 30 days following an infusion of adimlecileucel and are potentially attributable to treatment on study. Toxicities which are attributable to underlying malignancy and/or were present prior to initiation of therapy will not be tracked. We will perform assessment of CRS and ICANs per institutional standards to align with FACT requirements. Please see section 17.2 for Serious Adverse Event reporting.

### 11.1 Identified risks

1. **Autoimmune Hemolytic Anemia.** Autoimmune hemolytic anemia has been reported in 2 out of 75 (2.6%) patients treated with CMV peptide-specific T-cells in prior phase 1 and phase 2 clinical study experience. Both SAEs were grade 3 events, and one event was considered possibly related to CMV peptide-specific T-cells while the other was considered to be unrelated. Patients who develop autoimmune hemolytic anemia should be managed per institutional standard. Discussion with the medical monitor is encouraged.
2. **Specific Immune Reactions.** The CMV peptide-specific T-cells are expected to migrate to sites where CMV infected cells are concentrated, and to begin to kill these CMV infected cell populations. These cells may be concentrated in the lung, liver, retina/central nervous system, or intestinal tract. While it is expected that the small doses of T-cells administered will take time to replicate, and will exert their antiviral effects over a time period of days to weeks, it is possible that these cells could concentrate in an infected tissue and cause more severe inflammation as they attack virus infected cells. This could transiently increase the severity of a pneumonia or a CMV-induced encephalitis, retinitis, hepatitis or intestinal infection, and could even be life-

threatening. Additionally, patients with pre-existing pulmonary conditions may be at increased risk for development of pulmonary toxicity including diffuse alveolar hemorrhage.

3. **Graft versus Host Disease.** See section 11.0

## 11.2 Theoretical risks

1. **Acute Toxicities, Allergic Transfusion Reactions, and Cytokine Release Syndrome.** The infusion of CMV-peptide specific T-cells might cause an acute transfusion reaction or an allergic reaction to the cell infusion manifested by any one or all of the following clinical signs and symptoms: fever, shaking chills, difficulty breathing, a drop in the blood pressure, skin rash or swelling of the mucus membranes in the mouth or vaginal tract, or impairment of kidney function. Based on prior experience with infusions of T-cells at our own and other institutions, the risk of such immediate toxicities is anticipated to be small. However, each patient will be closely monitored for vital signs and clinical symptoms prior to and following T-cell infusion. Reactions will be treated as clinically indicated. Similarly our prior experience and that of other centers predict that the risk of cytokine release syndrome which is characterized by fever or an allergic reaction to the cell infusion manifested by is low. Patients developing fever after infusion of ATA230 will be assessed for other evidence of cytokine release syndrome and treated for it as per institutional guidelines.
2. **Infection.** There is a potential that transfusions of white cells or T-lymphocytes may also serve as vectors of serious infection. All precautions to maintain sterility will be taken.
3. **Marrow Allograft Rejection.** Patients receiving third party donor-derived CMV specific T-cell infusions for treatment of CMV infection may be at risk of an acute rejection episode following infusion of the T-cells. This risk is expected to be very low, since these T-cells only transiently engraft. Indeed, rejections have not been observed in either marrow or organ allograft recipients

treated with third party EBV-specific T-cells (31, 41). Such episodes could be precipitated if significant numbers of alloreactive T-cells are present in the T-cell inoculum. In allogeneic hematopoietic cell transplant recipients, this could lead to loss of the hematopoietic cell transplant, resulting in marrow aplasia, a potentially lethal complication. Therefore, if severe leukopenia or thrombocytopenia is observed that is potentially attributable to the infused T-cells, the patient will be treated with prednisone and/ or anti-thymocyte globulin to eliminate the infused third party T-cells.

## **12.0 CRITERIA FOR THERAPEUTIC RESPONSE/OUTCOME ASSESSMENT**

The primary endpoint of this study is to assess whether the infusion of adimleculeucel has therapeutic activity in curing CMV infections in recipients of HCT, SOT recipients, HIV, other immunocompromised states or immune competent subjects who require therapy. This study specifically will evaluate the therapeutic efficacy and persistence after infusion of adimleculeucel derived from third party donors for the treatment of CMV infections. The second clinical end point of this study is safety, especially the evaluation of GvHD induction after infusion of the third party adimleculeucel.

The responses of CMV infections will be clinically monitored as detailed under section 10. Responses to adoptively transferred T-cells are usually not observed until the T-cells have had time to expand within the transplant recipient, a period of at least 3 days, and as many as 18-21 days after the T-cell infusion. Final responses will be captured in CRDB and scored between days 28-42 post the final infusion of each cycle. Such window of evaluation ends the first day of the following cycle if patient switches cell lines and overlaps days 28-42. Best response observed in the full course of treatment will also be recorded as a distinct entity.

**Clinical responses** will be considered complete if all manifestations of CMV disease have resolved and/or the patient no longer has detectable CMV DNA by PCR.

**Partial response** will be defined as a  $2 \times \text{Log}_{10}$  reduction in the level of CMV DNA detected in the patients blood and/or improvement in clinical parameters of CMV infection such that the patient is symptom-free. For patients with a baseline CMV PCR  $< 13,800$  copies/mL a partial response will be defined as having a CMV PCR of  $< 137$  copies/mL on two occasions during the assessment period.

**Stable disease** will be defined as no change in the clinic severity of disease in any organ and CMV DNA is decreasing by the time of the evaluation time point but may be higher than the baseline CMV PCR (reflecting an increase that can occur during in vivo expansion of CMV-CTLs) and has not decreased by  $2 \times \text{Log}_{10}$ .

**Progressive disease** will be defined as disease progression by clinical and radiologic parameters, ascribable to CMV infection in any affected organ, will unchanged or increased levels of CMV DNA.

Patients lost to followup either during therapy or followup or patients with changes in antiviral therapy during treatment with adimleculeucel such that any changes in the extent of CMV viremia or disease cannot be attributed to cellular therapy will be defined as not evaluable for outcome assessment. Patients evaluable for some but not all cycles of cellular therapy will be evaluated as such.

Graft versus Host Disease initially developing 10 to 100 days post T-cell infusion will be considered to be potentially ascribable to the T-cell infusion. Graft versus Host Disease will be diagnosed and clinically graded using the standard criteria of the IBMTR/NMDP Consensus Panel. Whenever,

possible, the diagnosis will be confirmed by biopsy of skin or other involved organ, using the pathological criteria of Woodruff et al. Patients with preexisting GvHD of grade 1 severity not requiring systemic steroids, or patients with a prior history of GvHD who have resolved this process sufficiently so that they no longer require parenteral steroid treatment will be considered to have developed an exacerbation or worsening of GvHD ascribable to the T-cell infusion if they redevelop clinical evidence of grade 2 or greater GvHD 7 to 100 days after a dose of T-cells.

For the evaluation of toxicities, the NCI Standard Toxicity Scale 4.0 will be employed.

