Of the 50 patients 18 had a complete and 14 a partial response for an overall response rate of 64%. Response rates in patients with disease (5CR+4PR/15) were similar to those of patients with persistent viremia (13CR+10PR/35). In patients treated for viremia alone, survival at 6 months was 65.7% and in those with disease 60.0% (a). More extensively pretreated patients who received CMVpp65 CTLs > 100 days post CMV initial detection fared as well as those treated earlier (62.1% vs. 66.7% OS) (b). Patients who responded to CMVpp65-CTL therapy (CR or PR) had an improved survival with 6 month overall survival of 81.3% (b) and 12 month overall survival of 62.1% (c); only 1 of these 32 patients died of CMV. In contrast 7 of 18 non-responding patients died of CMV; overall survival in this cohort was 33.3% at 6 months. By 12 months, 8 non-responding patients had died of CMV and overall survival had decreased to 22.2%.

Toxicities associated with CMVpp65-CTL infusions in this cohort are limited with 5 patients experiencing adverse events of > grade 3 severity deemed possibly related to CMVpp65-CTL therapy. Two of these patients died, one due to sepsis and one due to progression of CMV.

This study demonstrates a high response rate among patients with otherwise refractory CMV viremia and disease. The bank of CMVpp65-CTLs can provide an immediate source of HLA partially-matched appropriately restricted T cells for adoptive immunotherapy to treat persistent CMV viremia and CMV disease, including disease isolated to the CNS. The availability of 3rd party CMVpp65-CTLs enables treatment early in the course of disease and may thereby improve response rates while minimizing toxicity from anti-viral therapy.

In addition to these on protocol patients, we have treated patients on single patient use/eINDs for refractory CMV occurring after SOT (N=2) and HIV (N=2). These patients have not experience a toxicity profile to suggest different toxicities than HCT patients who have received CMVpp65-CTLs and no serious adverse events were submitted.

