### 9.1 Treatment with adimleculecel

This study will enroll subjects regardless of the underlying susceptibility to CMV, including alloHCT, SOT, human immunodeficiency virus, other immunocompromised states, and immune competent subjects who require therapy. Subjects must have active CMV viremia or disease for  $\geq 2$  weeks

despite treatment with antiviral therapy or must be intolerant to antiviral therapy due to treatment-related toxicity or comorbidities such as renal insufficiency or myelosuppression.

Subjects will receive adimleculeucel from cell lines generated from normal alloHCT donors or healthy donors, specifically consented for this purpose, based on having a partial match of  $\geq 2$  HLA alleles shared between the donor and the subject including the HLA restricting allele of the adimleculeucel cell product.

Adimleculeucel will be administered in cycles lasting 5 weeks (35 days). During each cycle, subjects will receive IV adimleculeucel at a dose of  $1 \times 10^6$  cells/kg (with an acceptable range of 0.8 –  $1.2 \times 10^6$  cells/kg) for 3 weeks or total dosing of  $2.4 - 3.6 \times 10^6$  cells/kg per cycle on days 0, 7, and 14. Tests quantitating CMV viremia by CMV DNA copies per milliliter of blood should be obtained weekly for the first 8 weeks post-initial infusion with CMV-specific T-cells, and then at approximately monthly intervals until 6 months post infusion.

Additional 3 week courses of adimleculeucel may be administered if patients have ongoing disease and/or levels of CMV DNA in blood are still detectable. These secondary courses will usually employ T-cells from the same third party donor. However, adimleculeucel derived from an alternate third party donor's CMV pp65-specific T-cells may be used if no further cells from the same donor are available or for patients with stable or progressive CMV infection refractory to antiviral drugs, since infusion of virus specific T-cells from a secondary donor specific for a different CMV peptide and restricted by the same or an alternate HLA allele shared by the recipient has, in several cases, induced durable regression of disease (23).

Subjects will generally be treated for a maximum of 2 cycles, though subjects achieving PR by the end of Cycle 2 may receive a third cycle. Subjects with PD at the end of Cycle 1 or later, or who experience unacceptable toxicity, will be offered Switch Therapy if appropriate.

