### **14.0 BIOSTATISTICS**

A phase 2 trial design will be applied to determine the efficacy and safety of adimlecleucel for the treatment of marrow transplant patients with CMV. The endpoint of this study is complete response or partial response, as defined in Section 12. It is anticipated that accrual will be completed within 3 years.

The study design for HCT recipients aims to detect between response rates of 0.40 and 0.56 in the population. This two-stage design has a target sample size of 69 evaluable patients. If 15 or fewer patients respond in the first 36 patients that are evaluable for outcome assessment, then the trial will be stopped. If at least 16 patients respond, then 33 additional patients will be accrued for therapeutic response assessment. At the conclusion of the trial, if 32 or fewer patient responses are observed, we will conclude that the treatment is not sufficiently active. This design has a power of at least 0.90 for a population CR/PR rate equal to 0.56 using a one-sided test with type 1 error rate of 0.10. To reach 69 evaluable patients, it is anticipated that 81 patients will be recruited.

Based on the limited data in the setting of SOT recipients as well as immune deficient and immune competent individuals, results for these patients will be analyzed separately and will be descriptive.

In order to reduce patient risk, the study design includes early termination in the event of excessive graft versus host disease or solid organ rejection, requiring addition of immunosuppressant therapy to doses above those at the time of enrollment on trial, during the accrual period. The calculation is based on a group sequential design in a single-arm trial with a binary outcome.

Failure type	# of failures needed to stop the study	Failure rate in the population	Probability boundary is crossed
Acute GvHD (grades 3-4)  Or solid organ transplant rejection	3 within the first 15 patients	0.06	0.10
	4 within the first 24 patients  5 within the first 35 patients  6 within 51 patients	0.20	0.90

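### As written, Section 12.0 scores persisting organ disease with cleared blood DNA as a complete response, and an unchanged load below 137 copies/mL as a partial response

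*Combined protocol and SAP*

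**What the plan says.** Section 14.0 defers entirely to Section 12.0 for scoring: "The endpoint of this study is complete response or partial response, as defined in Section 12". It adds no rule of its own.

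In Section 12.0, a response "will be considered complete if all manifestations of CMV disease have resolved and/or the patient no longer has detectable CMV DNA by PCR". Partial response is a 2 log10 fall in blood CMV DNA "and/or improvement in clinical parameters of CMV infection such that the patient is symptom-free". Both definitions apply to all patients; neither separates those treated for organ disease from those treated for viremia alone.

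A special rule covers low loads. For a baseline under 13,800 "copies/mL a partial response will be defined as having a CMV PCR of" less than 137 "copies/mL on two occasions during the assessment period". This rule has no clinical limb, no required change and no lower bound on the baseline.

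Section 6.1.1 admits a patient on a documented CMV illness alone. Microbiological evidence is an alternative first criterion, and no minimum copy number is set for either route.

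Section 3.0 describes how 50 earlier recipients of third-party cells were scored, and there the rule did depend on presentation. A disease patient needed virus gone from every site and from blood for CR, and resolved symptoms plus a virologic PR for PR. Sections 12.0 and 14.0 do not refer to that rule.

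**The concern.** The CR plus PR count decides the trial. For HCT recipients it stops at 15 or fewer responders among the first 36 evaluable patients, and the treatment is called active at 33 or more of 69. One patient scored differently can turn 32 into 33.

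Two kinds of patient can be counted as responders without benefit in the condition that brought them in. The first has organ disease that persists while blood DNA becomes undetectable. The second enters with organ disease and a load already below 137 copies/mL and stays there. Section 3.0 says the cell bank can be used "to treat persistent CMV viremia and CMV disease, including disease isolated to the CNS", so disease confined to one site is within the plan's own experience, although blood levels for those patients are not given.

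If the team in practice scores by presentation, its count can differ from the count that Section 12.0 yields, and the protocol would not show which was used.

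**Working it through.** **1. The plan's own design figures.** Inputs from Section 14.0: 36 then 69 evaluable patients, continue at 16 or more, active at 33 or more, rates 0.40 and 0.56. The exact probability of declaring activity is the sum over x = 16 to 36 of P(Bin(36, p) = x) × P(Bin(33, p) ≥ 33 − x).

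- p = 0.40: 0.0999 (stated type I error 0.10)
- p = 0.56: 0.9001 (stated power at least 0.90)

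Both reproduce, so the design is sound if 0.40 and 0.56 are response rates on the Section 12.0 definition.

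**2. Two patients scored by Section 12.0 as written.**

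| Patient | CR | PR | Stable disease | Progressive disease |
|---|---|---|---|---|
| A: colitis persists; DNA falls by more than 2 log10 to undetectable | Met by the DNA limb | Also met | Excluded: DNA has fallen by 2 log10 | Excluded: DNA has fallen |
| B: organ disease unchanged; 100 copies/mL at entry and at two readings in the window | Not met | Met by the 137 rule | Not met: DNA is not decreasing | Not met: no clinical progression |

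For A, no non-response category is available. For B, PR is the only category that fits. Two readings are feasible: scoring falls 28 to 42 days after the last infusion of the cycle, which is days 42 to 56 when that infusion is on day 14, and the schedule has weekly PCR to week 8.

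**3. Fall required by the low-load rule.** Required fall = log10(baseline / 137).

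| Baseline (copies/mL) | Required fall (log10) |
|---|---|
| 13,800 | 2.00 |
| 1,370 | 1.00 |
| 1,000 | 0.86 |
| 300 | 0.34 |
| below 137 | none |

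Since 13,800 / 100 = 138, the rule joins the general 2 log10 rule at its upper end. The required fall shrinks as the baseline falls and disappears below 137.

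**4. Size of the first gap in the one series available.** From Section 3.0, 15 of 50 patients had organ disease, with 5 CR and 4 PR. Disease non-responders = 15 − (5 + 4) = 6, and 6 / 50 = 12%. That is the most that could have moved from non-responder to responder by this route. The 4 disease PRs might also have become CRs, but that leaves CR plus PR unchanged. This is a ceiling in that series, not an estimate for this trial.

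**The case against.** *Clinicians will read the limbs by presentation.* This is plausible, and the Section 3.0 series was scored that way. Some of those patients may even belong to this trial, which the documents do not settle. If so, the defect is that Section 12.0 does not carry the team's rule. It remains a defect, because Section 14.0 points to Section 12.0 and nowhere else.

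*Other sections show the intent.* Section 9.1 says further courses "may be administered if patients have ongoing disease and/or levels of CMV DNA in blood are still detectable", which lists disease and blood DNA separately. But it is a re-treatment rule, and Section 4.2 ties further courses to detectable blood DNA. Neither settles scoring. Objective 1a in Section 2.0 asks for a decrease in viral load, which argues against counting an unchanged low level, but the scoring rule does not say so.

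*The 137 threshold may reflect the assay.* If 137 lies near the limit of quantification (an assumption; the limit is not given), a larger fall from a low baseline could not be measured. This stands against criticising small falls from baselines above 137, and none is claimed as an error here. It does not remove patient B, who shows no change. No document shows that such a patient has been enrolled.

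*Stronger inferences that the documents do not support:*

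- That the type I error is inflated. This needs a misclassification rate, which is not given, and presumes that 0.40 was set on a stricter definition.
- That resolved disease with persisting viremia is wrongly counted. It meets objective 1b.
- That the low-load rule is looser than the 50% test applied to two PRs in the earlier series. That test depended on the testing method, so a common scale cannot be assumed.
- That viremia-only patients below 137 can respond only by CR. Nothing in the documents says so.

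**Conclusion.** The concern holds on the current text in two parts: the and/or definitions are not assigned to entry groups, and the low-load PR rule can be met with no change from baseline. Following Section 12.0 literally can therefore give a responder count that does not measure response. This should be fixed before the endpoint is analysed.

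How often it matters is unknown, because neither the baseline loads nor the assay limit is given. The only bound is for the first part: responder status could have changed in at most 6 of the 50 earlier patients. The sample size, stopping rule and stated error rates are not challenged. Their validity does depend on 0.40 and 0.56 having been set on the definition that is finally used.

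**What to change.** For scoring the Section 14.0 endpoint, Section 12.0 should state:

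- **Organ disease at entry:** not a responder on blood DNA alone while disease manifestations persist. This is judged on clinical assessments already scheduled or done as clinically indicated, with no added biopsy. The earlier series' CR rule relied on biopsy, and Section 10.2.3 collects tissue only where indicated and possible, so that rule should not be imported whole.
- **Viremia only at entry:** scored on the virologic criteria.
- **The 137 rule:** applies only when the baseline is 137 copies/mL or above. Disease patients below that are scored on the clinical limb. The sponsor states how any viremia-only patient below 137 is scored, in light of the assay limit.

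Section 14.0 should confirm which definition 0.40 and 0.56 were set on. The report should give the responder count under both the current and the clarified wording, including patients already assessed.

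The cost is a few sentences and a second scoring of assessed patients; no new tests are needed. There are three downsides. The response rate may come out lower. The clarification is made during an open single-arm trial, which is why both counts should be reported. The scoring definition may also differ from the response categories in the Section 9.1 action table, which the sponsor should reconcile. No treatment rule is proposed.
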